3.2. Selection of Doses

3.2.1. Experimental Treatments

3.2.1.1. For the Study

The dosage regimens of DS-5565 (15 mg QD and 15 mg BID) were selected based on the results of the completed Phase 2 study in the US of DS-5565 in subjects with DPNP (DS5565-A-U201) as well as dose optimization modeling and simulation. In the DS5565-A-U201 study, efficacy was observed across a dose range from 15 mg QD to 15 mg BID. To confirm the DS5565-A-U201 experience in subjects with FM and to determine whether subsets of subjects may respond better to 15 mg QD or 15 mg BID, both doses are being evaluated in the preceding Phase 3 studies (DS5565-A-E309, DS5565-A-E310, or DS5565-A-E311).

The results of the DS5565-A-U201 study (Section 1.1.1.5) suggest that 15 mg QD may be the minimum effective dose, while efficacy is similar but numerically better at the 15 mg BID dose compared to 15 mg QD. Overall, there were greater mean reductions from baseline to end-of-treatment (Week 5) in ADPS in the DS-5565 treatment groups compared to placebo, especially at the higher dose levels. The mean changes from baseline to Week 5 in ADPS were -2.04, -2.32, -2.66, -2.64, and -2.79 for the DS-5565 5 mg QD, 10 mg QD, 15 mg QD, 10 mg BID, and 15 mg BID treatment groups, respectively, compared to -1.86 for placebo. These treatment differences were statistically significant ($p < 0.05$) at the DS-5565 15 mg QD, 10 mg BID, and 15 mg BID dose levels.

Both of the Phase 3 dose regimens (15 mg QD and 15 mg BID) have a safety profile that is consistent with the $\alpha_2\delta$ ligand class of drugs; AEs have generally been mild to moderate in severity (see the DS-5565 Investigator Brochure). The DS-5565 30 mg/day treatment arm will be titrated from 15 mg/day after three weeks to lower the potential risk of side effects in subjects who require the higher dose for effective pain relief. No dose adjustment will be made for subjects with mild renal impairment, as only small increases in area under the concentration time curve (AUC) (1.4-fold) and maximum plasma concentration (C_{max}) (24%) were observed in healthy subjects with mild renal impairment ($CrCl$ 50 to 80 mL/min/1.73 m² [refer to DS-5565 Investigator Brochure]).

The data from DS5565-A-U201 were also modeled for insights into dose optimization. Efficacy was determined using weekly ADPS. A continuous bounded outcome score methodology was employed.² Two safety endpoints, dizziness and somnolence, were modeled. A time-to-(first) adverse event was modeled (hazard model) as well as severity of AE, conditional on having an event (ordered categorical). These were fitted independently.³ According to this pharmacokinetic (PK)/pharmacodynamic (PD) modeling, total daily doses > 20 mg are required to achieve a difference in mean ADPS

of at least 1.0 point between DS-5565 and placebo. Total daily doses < 20 mg are not predicted to achieve this level of response. The predicted probability of achieving a true -1 ADPS difference for 30 mg/day (15 mg BID) is 0.501 (or about 50%) based on the model. A second dose (15 mg QD) was picked based on a lower target with an implied safety (i.e. lower risk of AEs such as dizziness) advantage.

A completed Phase 2 study in Asia (Japan, Korea, and Taiwan) of DS-5565 in subjects with DPNP (DS5565-A-J202) did not show statistically significant differences in mean changes in the primary efficacy parameter, ADPS, from baseline to end-of-treatment (Week 7) for the DS-5565 treatment groups (5 mg BID, 10 mg BID, and 15 mg BID) compared to placebo (Section 1.1.1.5). There was, however, a trend toward improvement for subjects treated with D-S5565 in terms of ADPS responder rate (i.e. proportion of subjects with $\geq 30\%$ and $\geq 50\%$ reduction in ADPS). The incidence of TEAEs showed potential dose-dependency (TEAEs occurred in 48.9% of subjects for the 5 mg BID group, 63.4% for the 10 mg BID group, and 73.3% for the 15 mg BID group).

3.2.1.2. For Individual Subjects

Subjects will be initiated at 15 mg QD. After 3 weeks of open-label treatment (i.e. at Visit 6), subjects may be titrated to 15 mg BID based on efficacy and safety criteria as detailed in Section 5.1.1. After a subject has been up-titrated to 15 mg BID, that subject may be down-titrated back to 15 mg QD based on efficacy and safety criteria as detailed in Section 5.1.1.

3.2.2. Control Treatments

No control treatments will be used in this study.

4. STUDY POPULATION

4.1. Enrollment

Subjects for this open-label extension study are those who completed participation (through the End-of-Tapering visit) in one of the preceding studies (DS5565-A-E309, DS5565-A-E310, or DS5565-A-E311) and agreed to rollover; In addition subjects who did not participate in a preceding double-blind study (referred to as de novo subjects) may be enrolled.

The investigator must inform each prospective subject of the nature of the study, explain the potential risks, and obtain written informed consent from the subject prior to performing any study-related screening procedures. For rollover subjects, signature of the informed consent document for this study should be obtained before the start of the End-of-Tapering visit (Week 14, Visit 13) of one of the preceding studies (DS5565-A-E309, DS5565-A-E310, or DS5565-A-E311). For additional information on informed consent, see Section 1.5.2.

The subject identification number used in the preceding study shall be retained for use in this study. Subjects who did not participate in a preceding study will be assigned a subject identification number. This subject identification number must be used for subject identification on all study-related documents (eCRFs, clinic notes, laboratory samples, etc.).

The user will need to supply the Interactive Voice Response/Interactive Web Response (IXRS) system with the information required by the system (e.g. site number, subject identification number).

A subject will be considered enrolled upon signature of the informed consent document for this study.

4.1.1. Inclusion Criteria

Subjects who completed one of the preceding Phase 3 DS-5565 study (DS5565-A-E309, DS5565-A-E310, or DS5565-A-E311)

Subjects must satisfy all of the following criteria to be included in the study:

1. Able to give written informed consent
2. Completed participation (i.e. completed the End-of-Tapering visit) in a preceding study of DS-5565 in FM (DS5565-A-E309, DS5565-A-E310, or DS5565-A-E311)
3. Women of child-bearing potential (WOCBP) must be using an adequate method of contraception (as detailed in Section 9.5) to avoid pregnancy during the study and for 4 weeks after study completion
4. The subject must not have experienced any significant safety issues during the preceding study that, in the investigator's judgment, would adversely impact the subject's well-being in the long-term extension

5. De Novo Subjects
6. Age \geq 18 years
7. Able to give written informed consent
8. Able to complete subject-reported questionnaires per the investigator's judgment
9. At screening, subjects must meet the 1990 American College of Rheumatology (ACR) criteria for FM, i.e. widespread pain present for at least 3 months and pain in at least 11 of 18 specific tender point sites. In addition, the 2010 ACR criteria must be met:
10. Widespread pain index (WPI) \geq 7 and symptom severity (SS) scale score \geq 5, or WPI 3 to 6 and SS scale score \geq 9
11. Symptoms have been present at a similar level for at least 3 months
12. The subject does not have a disorder that would otherwise explain the pain
13. ADPS of \geq 4 on the 11-point numeric rating scale (NRS) over the past 7 days prior to first dose (based on completion of at least 4 daily pain diaries during the 7-day baseline period)
14. Subject must have documented evidence of a fundoscopic examination (with pupil dilation) or a scanning laser ophthalmoscopy examination within 12 months prior to screening or at screening
15. Women of child-bearing potential (WOCBP) must be using an adequate method of contraception (as detailed in the body of the protocol) to avoid pregnancy during the study and for 4 weeks after study completion

4.1.2. Exclusion Criteria

All Subjects

1. Clinically significant unstable neurologic, psychiatric, ophthalmologic, hepatobiliary, respiratory, or hematologic illness or unstable cardiovascular disease (e.g. severe hypotension, uncontrolled cardiac arrhythmia, or myocardial infarction) or any other concurrent disease during the preceding study (for rollover subjects) or within 12 months prior to screening (for de novo subjects) that in the opinion of the investigator would interfere with study participation or assessment of safety and tolerability
2. Subjects who are at risk of suicide as defined by their responses to the C-SSRS or in the opinion of the investigator. Note: Subjects answering "yes" to any of the questions about active suicidal ideation/intent/behaviors occurring within the past 12 months must be excluded (C-SSRS Suicide Ideation section – Questions 3, 4, or 5; C-SSRS Suicidal Behavior section, any of the suicide behaviors questions). Such subjects should be referred immediately to a mental health professional for appropriate evaluation.

3. Subjects who are unlikely to comply with the protocol (e.g. uncooperative attitude, inability to return for subsequent visits) and/or otherwise considered by the investigator to be unlikely to complete the study
4. Subjects with severe or uncontrolled depression that, in the judgment of the investigator, makes the subject inappropriate for entry into the study
5. Subjects with pain due to other conditions (e.g. DPNP or post-herpetic neuralgia) that, in the opinion of the investigator, would confound assessment or self-evaluation of the pain associated with FM
6. Subjects with pain due to any widespread inflammatory musculoskeletal disorder (e.g. rheumatoid arthritis, lupus) or widespread rheumatic disease other than FM.
7. Abuse or dependence of prescription medications, street drugs, or alcohol within the last 1 year
8. Any history of a malignancy other than basal cell carcinoma within the past 5 years
9. A diagnosis of untreated sleep apnea or initiation of treatment for sleep apnea within the past 3 months
10. Known hypersensitivity to $\alpha_2\delta$ ligands or other components of the study medications
11. Pregnancy or breast-feeding, or intent to become pregnant during the study period
12. Abnormal investigative tests (i.e. ECGs) and laboratory values judged by the investigator to be clinically significant at the End-of-Treatment visit (Visit 11, Week 13) in the preceding study (for rollover subjects) or at screening (for de novo subjects), with particular focus on:
 - Abnormal renal function defined as calculated CrCl < 60 mL/min determined by the central laboratory using the Cockcroft-Gault equation,⁴ blood urea nitrogen > 1.5 × ULN; serum creatinine > 1.6 mg/dL (> 141.4 μmol/L); or
 - Abnormal liver function defined as AST (SGOT) > 2.0 × ULN, ALT (SGPT) > 2.0 × ULN; alkaline phosphatase > 1.5 × ULN; total bilirubin > 1.2 × ULN. If a subject has total bilirubin > 1.2 ULN, unconjugated and conjugated bilirubin fractions should be analyzed and only subjects documented to have Gilbert's syndrome may be enrolled; or
 - Creatine kinase > 3.0 × ULN

For De Novo Subjects Only

13. Unable to undergo pre-study washout of prohibited concomitant medications (as listed in Section 5.2.1 of the protocol)
14. Current severe or uncontrolled major depressive disorder or anxiety disorders as assessed by the Mini-international Neuropsychiatric Interview (MINI) interview (Version 6.0) at screening are excluded, but mild to moderate major depression or

anxiety disorders are permitted provided that the investigator assesses the patient as clinically stable and appropriate for entry into the study

15. Any diagnosis of lifetime bipolar disorder or psychotic disorder
16. Subject is currently enrolled in or has not yet completed at least 30 days since ending another investigational device or drug study or is receiving other investigational agents
17. Subject is an employee of the study center, an immediate family member* of an employee of the study center, or an employee of Daiichi Sankyo, INC Research, or any of the study vendors supporting this study. *(spouse, parent, child, or sibling, whether biological or legally adopted)

4.1.3. Women of Child-Bearing Potential

For the purposes of this study, all female participants will be considered as WOCBP unless they have undergone surgical sterilization or are postmenopausal and have a documented serum follicle stimulating hormone level >35 mIU/mL (with or without hormone replacement therapy) and no menses within the previous 12 months.

WOCBP are permitted in the study but must consent to avoid becoming pregnant by using an approved contraception method throughout the study and for up to 4 weeks after completion, as described below.

Study-acceptable methods of birth control are double-barrier methods, which include a combination of any 2 of the following: systemic contraceptives, diaphragm or sponge with spermicide, condom, intrauterine device or partner's vasectomy.

All female subjects, regardless of child-bearing potential, must have a negative serum pregnancy test at all clinic visits through to the End-of-Tapering visit. All incidence of borderline pregnancy tests (as reported by the central lab) at screening should be followed up to exclude pregnancy (Exclusion criteria 11). Exclusion criteria (Section 4.1.2) can be satisfied in the cases of

1. Documented permanent sterilization, methods which include hysterectomy, bilateral salpingectomy and bilateral oophorectomy.
2. Confirmation of postmenopausal status, with documented serum follicle stimulating hormone level >35 mIU/mL (with or without hormone replacement therapy) and no menses within the previous 12 months before Randomization Period.

A urine pregnancy test will be performed for all WOCBP at the Follow-Up clinic visit.

Daiichi Sankyo must be notified of any study subject who becomes pregnant while participating in this clinical study, as described in Section 9.5.

4.2. Removal of Subjects From Therapy

Data from all enrolled subjects are important to achieve study objectives, and subjects should be encouraged to adhere to protocol instructions and visit schedules. However, in accordance with the Declaration of Helsinki and other applicable regulations, a subject has the right to withdraw from the study at any time, and for any reason, without

prejudice to his or her future medical care by the study physician or at the study site. The investigator is also free to terminate a subject's involvement in the study at any time if the subject's clinical condition warrants such action. The sponsor or regulatory authorities also may request termination of the study at any time due to safety issues or concerns related to study conduct.

NOTE: In this study, the C-SSRS will be administered at all clinic visits. Based on the C-SSRS and investigator judgment, if a subject is identified as being at risk for suicide, appropriate safety measures should be implemented (see Section 3.1.6.1.2).

The MINI and C-SSRS are to be administered at any time during the study (including unscheduled visits) based on investigator's discretion (Section 3.1.6.1.2).

4.2.1. Reasons for Withdrawal/Early Discontinuation

If a subject discontinues from the study treatment for any reason, the reason for discontinuation or withdrawal must be recorded on the eCRF using the following criteria:

Subjects who did not complete one of the preceding Phase 3 DS-5565 studies (DS5565-A-E309, DS5565-A-E310, or DS5565-A-E311) and withdraw prior to start of treatment but after signing informed consent

- Did not satisfy all inclusion/exclusion criteria
- Adverse event
- Lost to follow-up
- Withdrawal by subject (indicate reason)
- Physician decision

For subjects discontinued or withdrawn after start of treatment but before completing the treatment period:

- Adverse event
- Death
- Lack of efficacy
- Lost to follow-up
- Protocol violation
- Study terminated by sponsor
- Withdrawal by subject (indicate reason)
- Other (indicate reason)

If a subject is withdrawn due to requirement for a prohibited pain medication, the reason may be recorded as lack of efficacy, as appropriate. Reasons recorded under "protocol violation" may include failure to comply with protocol requirements or study procedures, pregnancy, etc.

A subject may be withdrawn due to non-compliance with any aspect of the protocol, as determined by the investigator and/or the sponsor's medical monitor or designee. Subjects who miss > 7 days of consecutive doses of study medication should be withdrawn from the study and early termination study procedures performed.

All subjects who are withdrawn should complete protocol-specified withdrawal procedures (see Section 4.2.2 and Section 6.4).

4.2.2. Withdrawal Procedures

If a subject withdraws (or is withdrawn) from the study, the investigator should complete and report all observations as thoroughly as possible up to the date of withdrawal, including the date of last treatment and the reason for withdrawal.

If the subject is withdrawn due to an AE, the investigator should follow the subject until the AE has resolved or stabilized.

All subjects who are withdrawn from the study should complete all end-of-treatment/early termination (Visit 21) procedures as soon as possible after early withdrawal (Section 6.4). All subjects who are withdrawn from the study should return for a post-treatment follow-up visit (Section 6.5).

4.2.3. Subject Replacement

Subjects removed from the study for any reason will not be replaced.

4.2.4. Subject Rescreening Procedures

Rescreening of subjects will not be permitted.

5. TREATMENTS ADMINISTERED

5.1. Investigational Products

The Investigator must ensure that the investigational product will be used only in accordance with the protocol.

The investigational product for this study is:

- DS-5565 15 mg tablets

5.1.1. Method of Assigning Subjects to Treatments and Blinding

Subjects entering into the open-label extension phase of the study will initially receive a 15 mg QD dose of DS-5565. After 3 weeks on the 15 mg QD dose (at Visit 6, Week 3), subjects will be asked about the adequacy of their pain control. Depending on their level of pain control and whether they have experienced any clinically relevant TEAEs since the previous visit, subjects may be dose-escalated to DS-5565 15 mg BID. The dose escalation criteria are defined in Table 5.1.

Table 5.1: Dose Escalation Criteria

Pain Control ^a	Clinically Relevant TEAE ^b	Dose Increase ^c
Inadequate	No	Yes
	Yes	No
Acceptable but not optimal	No	Yes
	Yes	No
Optimal	No	No
	Yes	No

^a Based upon the investigator's judgment

^b Any moderate or severe episode of dizziness or somnolence, any episode of edema or clinically significant weight gain, or any other clinically relevant (in the judgment of the investigator) TEAE since the previous visit

^c Yes = subject may be dose-escalated to DS-5565 15 mg BID

Abbreviations: BID = twice daily, TEAE = treatment-emergent adverse event

Once a subject has been dose-escalated to 15 mg BID, continuation of the 15 mg BID dose will occur as long as pain control is adequate and the subject experiences no moderate or severe episode of dizziness or somnolence, edema, clinically significant weight gain, or any other clinically relevant (in the judgment of the investigator) AE. If the subject does experience a clinically relevant AE, then the following criteria will determine whether discontinuation or down-titration of the dose should occur:

- If the subject previously reported inadequate pain control with 15 mg QD dosing, the subject will be discontinued from the study
- If the subject previously reported acceptable pain control with 15 mg QD dosing, the subject may be dose-reduced to 15 mg QD

No blinding will be used.

5.1.2. Method of Assessing Treatment Compliance

Records of treatment compliance for each subject will be kept during the study. The identification number of all dispensed and returned study drug wallets should be recorded, along with the subject identification number (SID).

Treatment compliance will be calculated by dividing the number of doses taken by the number of doses assigned for the appropriate visit interval (adjusted for any changes in the visit interval). Compliance for each visit interval is defined as taking at least 80% of the study drug dosage prescribed for that interval. If a subject is noncompliant, the subject will be counseled by study staff on the importance of taking the correct amount of study medication.

Contract research organization (CRO) personnel will review each subject's treatment compliance during investigational site visits and at the completion of the study.

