1.3. Risks and Benefits for Study Subjects

The results from nonclinical and clinical studies suggest that subjects treated with DS-5565 may experience improvement in pain associated with FM.

Anticipated risks of DS-5565 include the occurrence of adverse reactions related to central nervous system depression, such as dizziness and somnolence, as well as peripheral edema. Other notable TEAEs that have been observed in Phase 1 and Phase 2 studies include elevations of hepatic transaminases and suicide. For the approved $\alpha_2\delta$ ligands, in addition to dizziness, somnolence, and peripheral edema, certain adverse reactions requiring caution have also been reported, including but not limited to: weight gain, ophthalmologic disorders, suicidal behavior and ideation, angioedema, hypersensitivity, abrupt or rapid discontinuation, abuse potential, congestive heart failure, renal failure, and creatine kinase elevations.

A detailed description of efficacy and safety data related to DS-5565, including the results of Phase 1 and Phase 2 clinical studies of DS-5565, is provided in the DS-5565 Investigator Brochure. Safety monitoring procedures described in the protocol are considered to be adequate to protect subject safety.

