6. STUDY PROCEDURES

A study visit schedule in tabular format is provided in [Appendix Section 17.3](#).

Subjects will receive open-label treatment for 52 weeks followed by 4 weeks of post-treatment follow-up. The screening/baseline process will depend on whether the subject is a rollover subject or de novo subject. De novo subjects will have a Screening visit (Visit 1) and also complete Visits 2 and 3 (as detailed in [Section 6.1.2](#)) before receiving study treatment at the Start-of-Treatment visit (Visit 4). Rollover subjects will have screening procedures performed at the Start-of-Treatment visit (Visit 4), which will occur on the same day as the End-of-Tapering visit of the preceding study (as detailed in [Section 6.2.1](#)). All subjects will visit the clinic the following week (Visit 5, Week 1); every 2 weeks thereafter for the next 12 weeks (Weeks 3, 5, 7, 9, 11, and 13); 3 weeks thereafter (Week 16); every 4 weeks thereafter for the remainder of the study (Weeks 20, 24, 28, 32, 36, 40, 44, 48, and 52); and at the post-treatment follow-up visit (Visit 23, Week 54). Post-treatment follow-up will also include telephone contacts at 3 days (Visit 22) and at 4 weeks (Visit 24) after the subject's last dose of study treatment.

NOTE: The MINI and C-SSRS are to be administered at any time during the study (including unscheduled visits) based on investigator's discretion ([Section 3.1.6.1.2](#)).

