a: The follow-up period will comprise a telephone contact 3 days after the last dose, a clinic visit at 2 weeks after the last dose (Week 54 if the subject completes treatment), and a telephone contact at 4 weeks after the subject's last dose of study treatment (Week 56 if the subject completes treatment).

b: For rollover subjects, informed consent will be obtained before the start of the End-of-Tapering visit in the preceding study and demography, height, and medical history will be used from the preceding study and will not be repeated. For de novo subjects, these assessments are not applicable at Visit 4.

c: For rollover subjects, any ongoing adverse events and concomitant medications should be recorded from the preceding study

d: For rollover subjects, values for vital signs, weight, C-SSRS, clinical safety laboratory tests, and pregnancy test will be taken from the End-of-Tapering visit of the preceding study and hence will not be repeated.

- e: A full physical examination will be performed at Visit 1 (for de novo subjects) or Visit 4 (for rollover subjects) and at Visit 21 (for all subjects). An abbreviated physical examination will be performed at Visits 5 to 20. Refer to Section 9.9.2 for details. Fundoscopy (for de novo subjects) will be performed at Visit 1 (with pupil dilation) or a scanning laser ophthalmoscopy examination, Visit 14 (without pupil dilation) or a scanning laser ophthalmoscopy examination, and Visit 21 (with pupil dilation) or a scanning laser ophthalmoscopy examination.
- f: A serum pregnancy test will also be performed for all women at all clinic visits (except as noted in footnote d) through the End-of-Treatment/Early Termination visit. A urine pregnancy test will be performed for all WOCBP at the Follow-up clinic visit.
- g: Subjects receiving 15 mg QD will be dispensed a 1-month supply (1 card). Subjects receiving 15 mg BID can be dispensed every 2 weeks (1 card) or monthly (2 cards).
- h: At Visit 20 (Week 48), subjects should be instructed to take all study medication, as scheduled, up until the day of their End-of-Treatment visit (Visit 21, Week 52), but not on the morning of Visit 21 (i.e. subjects should complete dosing on the evening prior to their End-of-Treatment visit).

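### The compliance rule in Section 5.1.2 has a floor of 80% but no ceiling, so intervals well above 100% are labelled compliant and do not trigger counselling

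*Combined protocol and SAP*

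**What the plan says.** Section 5.1.2 defines the measure: "Treatment compliance will be calculated by dividing the number of doses taken by the number of doses assigned for the appropriate visit interval", with an adjustment if the interval changes. The classification follows: "Compliance for each visit interval is defined as taking at least 80% of the study drug dosage prescribed for that interval". The consequence is: "If a subject is noncompliant, the subject will be counseled by study staff on the importance of taking the correct amount of study medication". No other section of the supplied text gives an upper limit or a threshold for taking too much.

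Three other places bear on the point.

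- **Class caution.** Section 1.3 lists reactions requiring caution with the approved drugs of the class, among them "abrupt or rapid discontinuation, abuse potential, congestive heart failure, renal failure, and creatine kinase elevations".
- **Supply.** Note g to the Schedule of Events (Section 17.3) reads: "Subjects receiving 15 mg QD will be dispensed a 1-month supply (1 card"). Subjects on 15 mg BID may be given one card every 2 weeks or two cards monthly.
- **Visits.** Section 6 sets a visit at Week 1, then "every 2 weeks thereafter for the next 12 weeks (Weeks 3, 5, 7, 9, 11, and 13"), then Week 16, then every 4 weeks to Week 52.

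**The concern.** The counselling text aims at the correct amount of medication, but the definition detects error in one direction only. A subject who misses a few tablets is noncompliant; one who takes double is compliant.

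This deserves attention because long-term safety is the primary objective and abuse potential is a named class caution. Section 9.3.2 also gives drug dependency or abuse as an example of an important medical event. QD and BID dosing use the same 15 mg tablet, so a subject assigned QD can reach the BID amount from a QD card for as long as the card lasts. Section 3.2.1.1 reports potential dose-dependency of treatment-emergent events in the Asian Phase 2 study (48.9%, 63.4% and 73.3% at 5, 10 and 15 mg BID), so the amount actually taken matters when events are interpreted. The rule that sorts subjects by tablet use should therefore not label a large excess as compliant.

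**Working it through.** The plan states no figure to reproduce. The check applies the Section 5.1.2 rule to tablet counts and then asks what the supply allows.

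**Rule.** Ratio = doses taken / doses assigned; compliant if the ratio is at least 80%; counselling if not compliant.

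**Step 1: classification in a 14-day QD interval (14 doses assigned).**

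| Tablets taken | Ratio | Label | Counselling required |
|---|---|---|---|
| 11 | 11/14 = 78.6% | noncompliant | yes |
| 12 | 12/14 = 85.7% | compliant | no |
| 21 | 21/14 = 150% | compliant | no |
| 28 | 28/14 = 200% | compliant | no |

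**Step 2: interval lengths (Section 6).** There is one interval of 1 week (Weeks 0 to 1), six of 2 weeks (Weeks 1 to 13), one of 3 weeks (Weeks 13 to 16) and nine of 4 weeks (Weeks 16 to 52): 1 + 12 + 3 + 36 = 52 weeks.

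**Step 3: what one card allows on QD.** The number of tablets per card is not stated, so 28 to 30 is assumed. Note g offers some support: if one card covers 2 weeks of BID dosing, it must hold at least 2 × 14 = 28 tablets. Also assumed are a fresh card at the start of the interval and visits on schedule. If the whole card is used:

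| Interval | 28 tablets | 30 tablets |
|---|---|---|
| 7 days | 400% | 429% |
| 14 days | 200% | 214% |
| 21 days | 133% | 143% |
| 28 days | 100% | 107% |

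Every entry is classed as compliant. Large excesses are possible in the 16 weeks of shorter intervals. In the 36 weeks of 4-week intervals, one card cannot carry a QD subject far above 100%.

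**Step 4: what an upper bound would catch, taking 120% as an illustration.** Over 14 days, 120% of 14 is 16.8, so 17 tablets (121.4%) would be flagged. Over 28 days, 120% of 28 is 33.6, so 34 tablets would be needed, which is more than the assumed card holds. The bound would therefore act mainly up to Week 16.

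**The case against.** The strongest reply is that the label carries little weight.

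- **The data exist.** The ratio itself is calculated for each interval and CRO staff review it (Section 5.1.2). Returned tablets are counted at each visit (Section 5.1.6). Dosing deviations must be notified to the sponsor promptly (Section 6.6).
- **Sites can act anyway.** Medication compliance and dosing instructions are reviewed at on-treatment visits (Section 6.3), and noncompliance with any part of the protocol can lead to withdrawal (Section 4.2.1).
- **No listed analysis uses the label.** Section 11.1 defines only enrolled and safety sets, and Sections 11.3 to 11.6 do not use compliance.
- **Further methods are deferred.** Section 11.2 leaves detail to a separate analysis plan that is not in the supplied text, so an exposure or overuse listing may be planned there.

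All of this stands. It rules out a stronger reading that a reader might infer: that the rule hides overuse, or conceals that an adverse event arose above the assigned dose. The documents do not support that, because the counts and the deviation reports remain whatever the label says. Nor do they support reading the rule as leaving overusers uncounselled: counselling is not required for them, but nothing prevents it.

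None of these provisions sets a threshold for overuse, changes the classification or triggers the counselling step. The gap in the definition remains.

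**Conclusion.** The point holds as a small defect in a stated rule: a 14-day interval at 200% is labelled compliant, while one at 78.6% leads to counselling. Overuse is unflagged, not lost, and no planned estimate or denominator changes.

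The feasible size is 200% to 214% for a full card used in a 14-day QD interval, and 100% to 107% in a 28-day interval. Both ranges rest on 28 to 30 tablets per card, a fresh card at the start of the interval and visits on schedule. A reader might infer that a QD subject could run at double the assigned amount for a whole 4-week interval; that does not fit one card per month. The documents do not show how many subjects would exceed 100%. Abuse potential is cited for the approved drugs of the class, not as an observed finding for DS-5565.

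This is a cheap improvement, not a threat to the study's conclusions.

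**What to change.** Add an upper bound to the compliance definition in Section 5.1.2, so that an interval above it counts as noncompliant and triggers the existing counselling step. The sponsor should set the value; 120% is only an example, and the documents give no figure. List the intervals above the bound separately, with assigned doses, tablets dispensed and tablets returned, for review as possible overuse.

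The cost is about one sentence and one listing, from counts already collected under Section 5.1.6. There are two limits. Lost or unreturned tablets will push some ratios over the bound, especially in the 7-day interval, where two extra tablets give 9/7 = 129%; flagged cases therefore need review, not automatic labelling as misuse. An interval ratio also cannot detect a subject who doubles the amount for 14 days of a 28-day interval and then runs out (28/28 = 100%), so the bound supplements deviation and adverse event reporting and does not replace them.
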